2.3 Primary, Secondary, and Exploratory Endpoint(s)

Primary endpoints:

- Rate of overall response (ORR) defined as sCR+CR+VGPR + PR as best response utilizing IMWG Uniform Response Criteria⁵⁵ calculated in the time period from initiation of study treatment until discontinuation of treatment

Secondary Endpoints:

[figure not shown]
- Adverse events, as graded by National Cancer Institute Common Terminology Criteria for Adverse Events (NCI CTCAE version 5.0), assessed from the initiation of study treatment until discontinuation of treatment
- Duration of response (DOR) defined as the duration from the date of initial documentation of a response (PR or better) according to the IMWG criteria to the date of first documented evidence of progressive disease according to the IMWG criteria or death due to PD whichever occurred first.
- Overall survival which is defined from the date of first dose of study treatment to the date of death due to any cause or censored based on the date of last encounter if patient is alive or lost to follow-up.
- Progression-free survival which is defined as the duration from the date of first dose of study treatment to the date of first documented evidence of progressive disease or death, whichever occurs first.
- Change in CD38 surface expression of plasma cells after azacitidine treatment (the CD38 expression of plasma cells pre and post first cycle of azacitidine treatment in this trial will be compared)
- Number of patients who achieve at least 1.5 fold increase in their CD38 expression by flow cytometry after azacitidine treatment
- Correlation of change in CD38 expression after azacitidine treatment to response including depth of response and duration of response

3 Study Design

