6.4 Correlative Studies

There will be two bone marrow biopsies performed for correlative studies. The first bone marrow biopsy will be performed within 14 days prior to the first azacitidine dose (during the screening phase) and the second bone marrow biopsy will be performed after completion of first 5 days of azacitidine treatment and prior to first dose of daratumumab treatment.

Refer to laboratory manual for specific specimen collection instructions. The correlative studies below and the analysis will be performed in batched samples. Samples will be retained and stored at the end of the study.

CD38 Expression Changes

Pharmacodynamic analysis of surface CD38 Expression on primary plasma cells (Secondary Objective)

Assessment of CD38 regulation with treatment of azacitidine in this study population is one of the secondary objectives of this study. Bone marrow (BM) samples will be collected as described above. BM mononuclear cells (MNCs) will be subject to ficol separation and stained with CD38-FITC, CD138-APC R700 and Propidium Iodide among other markers. Cells will be washed with PBS, resuspended in 5% FBS-PBS and analyzed by flow cytometry on BD Cytoflex. CS&T (Becton Dickinson) and Rainbow calibration beads (Spherotech) will be used to calibrate the instrument and fluorescence intensity of sequential samples. MFIs will be calculated on Flow Jo software. This will be done in [name] laboratory. Please see [Section 8.2.5.1](#) for further details on analysis.

Methylation Pattern Changes

Analysis of methylation pattern changes induced by Aza on primary plasma cells (Exploratory Objective, contingent upon funding)

Assessment of methylation of plasma cell whole genome and CD38 specific genome will be performed via whole genome reduced representation bisulfite sequencing in collaboration with Zymo Research. BM samples will be obtained before and after exposure to Aza and DNA will be extracted via the Quick DNA miniprep kit (Zymo Research). 200ng of genomic DNA will be bisulfite converted using EZ DNA Methylation-Gold Kit (Zymo Research). Subsequently, a region of the CD38 CpG island will be PCR amplified and cloned into the TOPO cloning vector (Life Technologies). Clones will be verified by PCR and 10 verified clones will be sequenced for analysis of CpG content and methylation levels.

Tumor Microenvironment Changes

Assessment of tumor microenvironment changes induced by Aza (Exploratory Objective, contingent upon funding)

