Secondary endpoints for efficacy will be assessed using duration of response (DOR), progression-free survival (PFS), and overall survival (OS). DOR is defined as the duration from the date of initial documentation of a response (PR or better) according to the IMWG criteria to the date of first documented evidence of progressive disease according to the IMWG criteria or death due to PD whichever occurred first. DOR for subjects who have not progressed will be censored at the last disease evaluation before the start of any subsequent anti-myeloma therapy. PFS which is defined as the duration from the date of first dose of study treatment to the date of first documented evidence of progressive disease or death, whichever occurs first. Participants without a disease assessment will be censored at the date of first study treatment received. OS will be calculated as the time from the first dose of study treatment until death from any cause. Participants who have not died will be censored at the last time the participant was known to be alive. Distributions of DOR, PFS, and OS will be summarized using the Kaplan-Meier estimator. For each secondary efficacy endpoint, median even-free survival will be reported and the corresponding 95% confidence interval will be calculated using Brookmeyer and Crowley method.

Correlative Studies Analysis

CD38 regulation by azacitidine (Secondary Endpoint)

Change in CD38 surface expression in MM patients treated with azacitidine will be summarized using descriptive statistics and tested using the one-sample t-test. Two-sided p-value less than 0.05 will be considered statistically significant. The proportion of patients with at least a 1.5 fold increase in CD38 expression after one cycle of azacitidine treatment will also be reported. This phase II sample size of 23 will provide >99% statistical power to detect a fold change of 1.965 (SD: 0.299) in CD38 surface expression of MM patients treated with azacitidine based on a one-sample t-test at a two-sided type I error rate of 0.05. This estimated change in CD38 surface expression was calculated from our preliminary pre-clinical data. The association between the fold change in CD38 expression post azacitidine treatment and depth of response and duration of response will also be evaluated using logistic regression, linear regression methods, and Spearman's correlation coefficient, as appropriate.

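### The CD38 t-test has no stated scale or null value; read naturally as raw fold change against 1, it leans modestly toward a false increase, and a log ratio removes this at no cost in power

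*Combined protocol and SAP*

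**What the plan says.** Section 2.3 lists the change in plasma-cell CD38 expression as a secondary endpoint and explains that "the CD38 expression of plasma cells pre and post first cycle of azacitidine treatment in this trial will be compared". It also lists the number of patients with at least a 1.5-fold increase. Section 6.4 makes the readout a flow-cytometry intensity from two marrow samples, one before azacitidine and one after its first five days: "MFIs will be calculated on Flow Jo software".

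Section 8.2 (Correlative Studies Analysis) sets the test: "Change in CD38 surface expression in MM patients treated with azacitidine will be summarized using descriptive statistics and tested using the one-sample t-test". The level follows: "Two-sided p-value less than 0.05 will be considered statistically significant". The only numerical description of the test is its power: "This phase II sample size of 23 will provide >99% statistical power to detect a fold change of 1.965 (SD: 0.299) in CD38 surface expression", "based on a one-sample t-test at a two-sided type I error rate of 0.05". The source of those figures is also given: "This estimated change in CD38 surface expression was calculated from our preliminary pre-clinical data". The same paragraph relates the fold change to depth and duration of response by logistic regression, linear regression and Spearman's correlation.

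Nowhere is the CD38 change defined as a ratio, a difference or a log ratio. No null value is written, and no log transform of CD38 is mentioned.

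**The concern.** A t-test needs a scale and a null value, and here both must be inferred. The power statement points to the raw fold change, for which no change would be 1.

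That pairing is awkward for a ratio of two noisy positive measurements. If azacitidine has no effect, the pre and post MFI are exchangeable and the log ratio is symmetric about 0. The raw ratio is right-skewed, however, and its mean lies above 1. A test of the mean raw ratio against 1 is then centred on the wrong value, and its errors lean toward an increase, which is the direction of the trial's hypothesis in Section 2.1.

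At stake is the trial's direct clinical check of its mechanism. A mean fold change, if reported, would be pulled upward in the same way. Leaving the scale open also lets it be chosen after the data are seen.

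**Working it through.** **Inputs from Section 8.2.** n = 23, two-sided 0.05, fold change 1.965, SD 0.299, one-sample t-test. A stop after Stage 1 (Section 8.1) would leave n = 13.

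**1. The plan's power.** Taking the null as 1 (an assumption, since none is stated), the noncentrality is (1.965 − 1)/0.299 × √23 = 15.5 on 22 df. Power exceeds 99.99%, so the stated figure is correct. It stays at or above 99% until the SD reaches about 1.03.

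**2. Mean ratio under no effect.** If log(post/pre) is normal with mean 0 and SD s, the mean raw ratio is exp(s²/2), which is above 1 whenever s > 0.

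**3. Values of s.** The plan's figures allow two:
- From its CV: √ln(1 + (0.299/1.965)²) = 0.151.
- Carrying SD 0.299 to a mean of 1: √ln(1 + 0.299²) = 0.293.

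For patients, I assume per-sample CVs of 20% to 50%. Then s = √2 × √ln(1 + CV²), and the mean ratio is 1 + CV².

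**4. Size of the nominal 5% test, n = 23, no effect** (simulation, at least 200,000 trials per row):

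| Source of s | s | Mean ratio | Total | False increase | Log-ratio test, total |
|---|---|---|---|---|---|
| Plan's CV | 0.151 | 1.01 | 5.6% | 4.1% | 5.0% |
| Plan's SD at mean 1 | 0.293 | 1.04 | 7.3% | 6.4% | 5.0% |
| Assumed CV 20% | 0.280 | 1.04 | 7.1% | 6.2% | 5.0% |
| Assumed CV 30% | 0.415 | 1.09 | 9.4% | 8.9% | 5.0% |
| Assumed CV 40% | 0.545 | 1.16 | 12.6% | 12.1% | 5.0% |
| Assumed CV 50% | 0.668 | 1.25 | 15.5% | 15.2% | 5.1% |

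The nominal rate in each direction is 2.5%. Repeat runs differ by a few tenths of a percentage point at most.

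**5. Sensitivity.**
- n = 13: 5.1% to 5.5% at the plan's SD, and about 7% at CV 50%.
- Heavier-tailed logs (t with 5 df), n = 23: 5.1% and 5.8% at s = 0.15 and 0.29; 8.0% at s = 0.5.
- Raw difference, post minus pre (assumed between-patient log-SD 0.7): 3.8% to 4.3% in total with balanced tails, so no inflation.

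**6. Estimation.** For a true median of 1.5-fold and s = 0.545, the arithmetic mean ratio is 1.5 × exp(0.545²/2) = 1.5 × 1.16 = 1.74.

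**7. Power on the log scale.** The planned effect is ln(1.965) − 0.151²/2 = 0.675 − 0.011 = 0.664. The noncentrality is 0.664/0.151 × √23 = 21.1, so power remains above 99.9%.

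**The case against.** The strongest reply is that the plan never says it will test a raw ratio against 1. A one-sample t-test of a change can equally be the paired test of post minus pre, which is not inflated, and a log analysis would also fit the words. This stands. A reader might infer that Section 8.2 specifies a wrong test. It does not: it specifies an incomplete one, and the raw ratio is only the reading that the power statement supports best.

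Second, the larger error rates are assumption-driven. A reader might infer an error rate of 10% to 15%, on the view that patient samples must vary more than the pre-clinical data. That is plausible but has no source in the documents. Section 6.4 provides bead calibration across sequential samples and batched analysis, which limit assay noise though not marrow sampling or biological variation. The part tied to the plan's own SD is about 6% to 7%, and less with 13 patients or heavy-tailed logs.

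Third, no decision depends on this p-value, and the 1.5-fold count would sit beside any small spurious mean. Both are true, although noise also feeds the count: at an assumed s of 0.5, about 21% of patients would reach 1.5-fold with no effect. Nor does Section 8.2 promise an arithmetic mean; its descriptive statistics could include medians.

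Finally, the lean depends on what null is meant. If the null is a mean raw ratio of exactly 1, the excess moves to the lower tail (3.3% to 9.4%, for s from 0.15 to 0.8). That null is not the no-effect state, however, because it requires the typical patient's CD38 to fall.

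**Conclusion.** The point holds as a gap in specification with a modest, conditional consequence. Scale and null value are missing. On the natural reading, with 23 patients, exchangeable lognormal MFIs and no effect, the total error is about 5.6% to 7.3% at the plan's SD. The excess is toward a false increase. It grows to about 15.5% only under an assumed per-sample CV of 50%, and it vanishes if a raw difference is tested.

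A reader might go further and infer that the power claim fails or that a real 1.965-fold effect would be misjudged. Neither follows: the power figure reproduces, and raw and log tests agree at that effect. The issue matters when the effect is small or absent, on a secondary endpoint. It does not touch the response-rate design or its stopping rule. It is worth correcting because the better analysis is free.

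**What to change.** In Section 8.2:
- Define the CD38 parameter for each patient as log(post MFI / pre MFI).
- State the null hypothesis of the one-sample t-test as a mean log ratio of 0.
- Report the geometric mean fold change with a back-transformed 95% CI.
- Use the log fold change in the logistic and linear regressions.

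Spearman's correlation is unaffected by the transform, and the 1.5-fold count stays as it is. If the sponsor intends a raw difference instead, the section should say so, and the power statement should be recast on that scale.

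The cost is a sentence or two of analysis text. No further samples or patients are needed, and power at the planned effect stays above 99%. The one visible downside is that the reported mean fold change becomes slightly smaller than an arithmetic mean would be.

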3.5 Duration of Follow Up

Each subject will be followed until 1 year after his/her last dose of study treatment, until death or withdrawal of consent for study participation, whichever occurs first. The end of study is defined as when all subjects have completed either at least 1 year of follow-up, or until death or withdrawal of consent for study participation, whichever occurs first. Further details regarding the long-term follow-up phase are detailed in [Section 6.3.3](#).

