2. Definite increase in the size of existing plasmacytomas or bone lesions. A definite increase is defined as a 50% (and at least 1 cm) increase as measured serially by the sum of the products of the cross-diameters of the measurable lesion
3. Hypercalcemia (>11.5 mg/dL; >2.875 mM/L)
4. Decrease in hemoglobin of more than 2 g/dL (1.25 mM) or to less than 10 g/dL
5. Rise in serum creatinine by more than or equal to 2 mg/dL (≥ 177 mM/L)
6. Hyperviscosity

In some subjects, bone pain may be the initial symptom of relapse in the absence of any of the above features. However, bone pain without imaging confirmation is not adequate to meet these criteria in studies.

Measurement of Endpoints for Response

The primary endpoint for response in this study is ORR as best response by the end of the study treatment. ORR is defined as the proportion of patients with stringent complete response (sCR), complete response (CR), very good partial response (VGPR), and partial response (PR) based on responses as assessed using the International Myeloma Working Group (IMWG) Uniform Response Criteria. Response evaluation will be performed on a monthly basis. Disease progression by paraprotein should be confirmed within the first 4 weeks after last assessment. DOR is defined as the time from the date of the first response to the date of subsequent PD or death due to PD, whichever happens earlier. In the absence of the confirmation of subsequent disease progression or death before the analysis cut-off date, the DOR will be censored at the date of the last valid assessment performed before the analysis cut-off date or date of initiation of new anticancer treatment, whichever is earlier. DOR is determined only for patients who have achieved a response of \geq PR. DOR will not be calculated for patients that do not achieve a response.

Assessment of Disease Progression or Response

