Disease progression must be consistently documented using the criteria in table in [Section 7.1.1](#). Disease progression based on 1 of the laboratory tests alone must be confirmed by at least 1 repeat investigation. Clinical judgment should prevail; however, repeat assessments after 1 to 3 weeks can be used as a general guideline. Disease progression based on imaging, bone marrow plasma cell percentage, or hypercalcemia (not attributable to any other cause) do not need to be confirmed. Bone marrow biopsy to assess morphology (aspirate and biopsy) at the time of progression will be at the discretion of the individual provider and not required by the study.

For subjects who discontinue study treatment before disease progression, disease evaluations should continue to be performed as described every 4 weeks until confirmed disease progression, death, the start of a new treatment for multiple myeloma, withdrawal of consent for study participation, or the end of study, whichever occurs first.

Methods of Response Evaluation

Response evaluation will include:

- M-protein quantification (serum and 24-hr urine)
- Serum free light chain (FLC) levels
- Bone marrow biopsy/aspiration (not required)

Myeloma Protein Measurements in Serum and Urine

Blood and 24-hour urine samples will be collected for serum quantitative IgGs, serum and urine M-protein measurements, serum and urine IFE measurements, and serum FLC assay in screening phase (within 28 days of first azacitidine administration). If urine samples cannot be collected, then serum markers will be used alone. Serum quantitative immunoglobulins, serum M-protein measurements, serum IFE, and serum FLC assay will be performed on Cycle 1 Day -7 (prior to first azacitidine dose), unless screening disease evaluation labs were performed within 14 days prior to this first azacitidine administration, and every subsequent cycle on D1 starting cycle 2 (disease evaluation labs do not need to be repeated on Cycle 1 Day 1) until off study and at EOT.

Blood (and 24-hour urine, as determined by the treating physician) samples for disease evaluation will be collected until the development of confirmed disease progression. Progression of disease based on serum markers will need to be confirmed by at least 1 repeat investigation. Progression of disease based on urine markers does not need to be confirmed. Clinical judgment should prevail; however, repeat assessments after 1 to 3 weeks can be used as a general guideline.

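### The plan does not say how a censored duration of response enters the regression and correlation methods named for its association with CD38 change, and the obvious ways of using those methods weaken the association

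*Combined protocol and SAP*

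**What the plan says.** Section 2.3 lists as a secondary endpoint: "Correlation of change in CD38 expression after azacitidine treatment to response including depth of response and duration of response". The method is in section 8.2, under CD38 regulation by azacitidine. For the association of fold change with depth of response and DOR, that paragraph ends: "duration of response will also be evaluated using logistic regression, linear regression methods, and Spearman's correlation coefficient, as appropriate".

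The plan treats DOR as censored time-to-event data in two places:

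- Section 8.2, secondary endpoints: "DOR for subjects who have not progressed will be censored at the last disease evaluation before the start of any subsequent anti-myeloma therapy". The distribution is then summarised by Kaplan-Meier.
- Section 7.1: without confirmed progression or death, "the DOR will be censored at the date of the last valid assessment performed before the analysis cut-off date", or at the start of new anticancer treatment if that is earlier.

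DOR exists for responders only: "DOR will not be calculated for patients that do not achieve a response". On follow-up, section 3.5 says "Each subject will be followed until 1 year after his/her last dose of study treatment", ending earlier at death or withdrawal of consent. For patients who stop treatment before progression, section 7.1 says "disease evaluations should continue to be performed as described every 4 weeks until confirmed disease progression", with other end points such as new myeloma treatment.

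No section names a Cox model, log-rank test, parametric survival regression, censored-rank method or landmark analysis for this association. None fixes the data cut-off for it.

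**The concern.** The methods do not match the form of the data. Kaplan-Meier handles censoring but takes no covariate. Logistic regression, linear regression and Spearman take a covariate but, in standard form, no censoring indicator. To run them on DOR someone must do one of three things: treat a censored time as a completed duration, leave out censored responders, or split DOR at a time point. The plan chooses none of these, and its closing qualifier selects within the list without adding to it.

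The longest responses are the ones most likely to be censored. Cutting them short or removing them therefore pulls the estimated association towards zero. At stake is a declared secondary endpoint that bears on the trial's mechanism (section 2.1: better response through CD38 upregulation). The choice of method, and with it the size of the loss, is left until the data are seen.

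**Working it through.** **The plan's own figures.** The CD38 paragraph's only power figure is for the change itself: standardised effect (1.965 - 1)/0.299 = 3.23, n = 23, two-sided 0.05. Power exceeds 0.9999, so the stated figure of more than 99% holds. The Simon design also reproduces (exact one-sided alpha 0.030, power 0.903). Neither bears on the association with DOR, for which the plan gives no figure.

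**How many patients have a DOR.** 23 × 0.33 = 7.6 at the target response rate and 23 × 0.08 = 1.8 at the null rate. At 33%, the probability of fewer than 5 responders in 23 is 0.08.

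**Inputs to the illustration.**
- From the documents: accrual over 8-12 months (section 8.4) or 12-18 months (section 3.1). Possible cut-offs are 18 months (section 3.6), 30 months (section 3.7) and 36 months (section 3.1) after opening to accrual. The median DOR of 7.6 months is for daratumumab monotherapy (section 1.2).
- Assumed: exponential DOR; hazard λ·exp(bz), with z the standardised CD38 change and b = ln 0.5; response 2 months after entry; uniform entry. A second median of 4 months is also assumed, near the 3.5-month PFS in section 1.3. The documents give no DOR after retreatment.
- Censoring time = cut-off - entry - 2 months. There are 400,000 responders per scenario, and the true Spearman is 0.50.

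**A check without simulation.** Write log T = -log λ - bz + log E, with E unit exponential. The observed log time is the smaller of log T and log c. Its derivative in z is -b if the event is seen and 0 if it is censored. For normal z the least-squares slope equals the average derivative, so slope = -b × P(event seen). The log-scale slope therefore falls by exactly the censored fraction. A separate simulation with true slope 2.0 agrees: 1.60 at 20% censoring (2.0 × 0.80), 1.28 at 36% (2.0 × 0.64) and 0.96 at 50% (formula 1.00).

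**Results, administrative censoring only** (range over accrual of 8, 12 and 18 months):

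| Median DOR | Cut-off | Censored | Raw slope falls | Log slope falls | Spearman, censored times used | Spearman, censored dropped |
|---|---|---|---|---|---|---|
| 7.6 | 18 | 37-53% | 80-88% | 37-54% | 0.434-0.291 | 0.236-0.222 |
| 7.6 | 30 | 18-25% | 59-68% | 18-25% | 0.486-0.465 | 0.337-0.306 |
| 7.6 | 36 | 13-18% | 50-58% | 13-18% | 0.492-0.483 | 0.370-0.344 |
| 4 | 18 | 20-37% | 61-75% | 19-37% | 0.479-0.364 | 0.330-0.303 |
| 4 | 30 | 7-11% | 34-44% | 7-11% | 0.494-0.489 | 0.423-0.393 |
| 4 | 36 | 4-7% | 26-34% | 4-7% | 0.495-0.493 | 0.445-0.425 |

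**No calendar cut-off**, independent random censoring of 5/10/20%, times used: Spearman 0.48/0.46/0.42, raw slope falls 15/27/46%, log slope falls 5/10/20%.

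**Logistic regression on DOR split at 6 months** (an example): 0-28% of responders cannot be classified at an 18-month cut-off, and none at 30-36 months.

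**Cox regression** returns a hazard ratio of 0.497-0.499 in every one of these large-sample scenarios.

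**At the trial's size** (8 responders, 12-month accrual, true hazard ratio 0.5, cut-offs 18-36 months):
- Expected events are 4.5-6.8 (median 7.6) or 5.9-7.6 (median 4).
- The 5th-95th percentiles of the Cox hazard ratio span about 0.05-1.4 at 18 months and 0.08-1.2 at 30-36 months. Between 0.3% and 4.3% of fits fail.
- The median estimate is 0.46-0.47. The geometric mean is 0.38-0.41, an overstatement of the effect.
- Power at two-sided 0.05: Cox Wald 0.03-0.14, Cox score 0.18-0.28, Spearman with censored times used 0.15-0.23. With no association the score test rejects in 5-7% of runs and Spearman in 5-6%.

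**The case against.** Four points can be made for the plan.

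1. *The named methods can be made to work.* This stands in part. A reader might infer that they cannot be applied to a censored DOR at all, but the documents do not support that. Logistic regression on a fixed-time split is a recognised route, and at 30-36 months administrative censoring leaves nobody unclassified at 6 months. The phrase on linear regression methods could also be stretched to accelerated-failure-time models. The plan states neither.

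2. *The large losses need an early analysis.* This stands. A reader might take the 80-88% fall as the expected loss, but it needs raw-scale regression and an 18-month cut-off, and no section ties this analysis to that date. Follow-up under sections 3.5 and 7.1 could remove much administrative censoring. Censoring for new therapy or withdrawal would remain.

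3. *Cox regression is no better with 8 responders.* This stands for the Wald test, which is very conservative here. It does not stand for the score test, which does at least as well as Spearman at a similar, slightly higher null rejection rate. Nor may one infer that Cox makes the question answerable: power stays below 0.3, and the estimate is imprecise and on average overstated.

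4. *Nothing depends on it.* This is correct for the trial's decisions. No stopping or rejection rule uses this association, which limits the priority of the point but does not supply the missing rule.

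**Conclusion.** The concern holds in a limited form. For a listed secondary endpoint, the plan names methods that in standard form ignore the censoring in its own DOR, and it does not say how censored responders enter. Used without such a rule, they attenuate the association. The loss is large for raw-scale linear regression, for dropping censored responders or for an early cut-off. It is small for Spearman with censored times used at 30-36 months.

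The sizes rest on an assumed exponential DOR, a hazard ratio of 0.5 per SD, 2 months to response, two illustrative medians and censoring unrelated to CD38. Only the direction, and the dependence on unstated choices, follow from the plan itself. A reader might infer that the efficacy conclusion is affected. It is not: response rate, sample size and the Simon rule do not use this analysis. With about 8 responders at the target rate and about 2 at the null rate, the result is exploratory whichever method is used.

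**What to change.** Change the CD38 paragraph of section 8.2 for DOR only:

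- Fit a Cox regression of DOR in responders on log2 CD38 fold change, using the plan's own censoring rules. Both marrow samples precede the first daratumumab dose (section 6.4), so the covariate is fixed before DOR starts.
- State the data cut-off as the end of the follow-up in section 3.5.
- Report the hazard ratio with a profile-likelihood 95% interval and a score or permutation test, not a Wald test, and label it exploratory.
- State the fallback in advance. With fewer than 5 events, or no convergence, list each responder's duration, censoring status and fold change without a model.
- Keep Spearman and logistic or ordinal regression for depth of response.

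The cost is wording: same samples, data and sample size. The downside is an imprecise hazard ratio that tends to overstate the effect at about 8 responders. With 8 responders and 12-month accrual, the probability of fewer than 5 events is 0.06 or less at 30-36 months, so the model would usually be fitted. It is 0.49 at 18 months with a 7.6-month median, which is a further reason to fix the later cut-off. At the null response rate the listing is the likely outcome.
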